1.0 TRIAL SUMMARY

Title	Phase I/II study of pembrolizumab in patients failing to respond to or relapsing after anti-CD19 chimeric antigen receptor modified T cell therapy for relapsed or refractory CD19+ lymphomas
Abbreviated Title	Pembrolizumab after CTL019/CTL119 for relapsed/refractory CD19+ lymphomas
Trial Phase	Phase I / II
Clinical Indication	Relapsed / refractory CD19+ B cell lymphomas after CTL019/CTL119
Trial Type	Investigator-initiated
Type of control	None. Enrollment will be offered to subjects with an unmet medical need, which is no available effective, standard therapy for relapsed / refractory CD19+ lymphomas
Route of administration	Intravenous
Trial drug, dose, route, regimen	Pembrolizumab (Keytruda [®]) 200mg fixed dose IV every 3 weeks
Trial Blinding	None
Treatment Groups	Single group
Number of trial subjects	12 evaluable subjects
Estimated enrollment period	12 months (approximately January 2016-January 2017)
Estimated duration of trial	36 months (approximately January 2016-January 2019)
Duration of Participation	24 months (12 months treatment + 12 months follow-up)
Objectives	
Primary Endpoints:
 
 1. Determine safety of pembrolizumab after CTL019/CTL119. This endpoint will be met if $\leq 30\%$ of patients develop toxicity resulting discontinuation of pembrolizumab. 2. Determine efficacy of pembrolizumab after CTL019/CTL119. This endpoint will be met if the ORR at 3 months is $\geq 35\%$.
Statistical methodology	
Primary Endpoints:
 
 1. Safety endpoint will be assessed using a Bayesian monitoring rule to ensure probability of a patient developing toxicity resulting in discontinuation of pembrolizumab $\leq 30\%$ 
Secondary Endpoints:
 
 1. ORR will be assessed using a one-sided binomial test 2. PFS, EFS, RD, and OS will be assessed using Kaplan Maier survival analysis. PFS after pembrolizumab will be compared to PFS after CTL019/CTL119 using a log rank test.

This document is confidential and the property of the University of Pennsylvania. No part of it may be transmitted, reproduced, published, or used by other persons without prior written authorization from the regulatory sponsor.

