4.2.3 Rationale for Endpoints

4.2.3.1 Rationale for Efficacy Endpoints

- 1) **Primary Objective:** To determine the safety of pembrolizumab in patients failing to respond to or relapsing after anti-CD19 chimeric antigen receptor modified T cell therapy for relapsed or refractory CD19+ lymphomas.

Although pembrolizumab has been approved for use in melanoma, there have been no studies in non-Hodgkin lymphoma and the transition to a fixed dose has not been well-studied. In previous studies of pembrolizumab, the rates of drug discontinuation due to an adverse event were 4.2% in melanoma and 2.6% in non-small cell lung cancer and the rates of drug discontinuation for any reason were 9.4% in melanoma and 21.1% in non-small cell lung cancer (see Investigator's Brochure). Additionally, given that we hypothesize that pembrolizumab may re-activate quiescent chimeric antigen receptor T cells, there is the potential for additional toxicity in patients who have previously received chimeric antigen receptor T cells. Thus, we will define safety as ≤ 30% of patients experiencing toxicities resulting in discontinuation of pembrolizumab.

This document is confidential and the property of the University of Pennsylvania. No part of it may be transmitted, reproduced, published, or used by other persons without prior written authorization from the regulatory sponsor.

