8.0 STATISTICAL ANALYSIS PLAN

8.1 Statistical Analysis Plan

8.1.1 Primary Objectives & Hypotheses

(1) Objective: To determine the safety of pembrolizumab in patients failing to respond to or relapsing after anti-CD19 chimeric antigen receptor modified T cell therapy for relapsed or refractory CD19+ lymphomas. Safety will be assessed by adverse event monitoring. Patients who have received at least one dose of pembrolizumab will be considered evaluable for safety. In this trial, success will be defined as receiving at least one dose of pembrolizumab and the lack at least possibly related adverse events leading to permanent discontinuation of pembrolizumab. Patients who experience Grade 3 or higher non-hematologic toxicity leading to permanent pembrolizumab discontinuation or any Grade 4 non-hematologic toxicity or cytokine release syndrome at least possibly related to pembrolizumab will be considered toxicity failures.

Methodology: We will use a Bayesian monitoring rule to assure that the failure rate is no greater than 30%. Monitoring will begin with the first patient. Because little information is available on the safety of this drug in lymphoma, we will assume a non-informative Beta(1, 1) prior distribution for the failure rate. We will denote the rate of pembrolizumab discontinuation as failure rate, FR, and will use the following monitoring rule in the interest of patient safety: we will stop the trial if at any time: $\Pr[\text{FR} > 0.30 \mid \text{data from the trial}] \geq 97.5\%$

That is, if at any time during the study, we can conclude that there is at least a 97.5% chance that the failure rate is greater than 30%, we will stop the study. The stopping boundaries corresponding to this probability criterion are to terminate the trial if:

$(\# \text{ of patients that experience failure}) / (\# \text{ of patients evaluated}) \geq 3/3, 3/4, 4/5, 4/6, 5/7, 5/8, 6/9, 6/10, 7/11, 7/12$. Any patient who has received at least one dose of pembrolizumab will be included in this denominator for evaluable patients if they have received at least 4 doses of pembrolizumab and not experienced toxicity OR if they have experienced any toxicity with any dose of pembrolizumab.

If the study is not terminated early, it will continue until all patients have been treated with pembrolizumab and completed all follow up evaluations.

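### Neither the 30% criterion nor the stopping rule measures support for a failure rate of at most 30%, although the primary safety claim needs that support

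*Combined protocol and SAP*

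**What the plan says.** **Criterion.** The synopsis (Section 1.0) lists safety first among the primary endpoints: "Determine safety of pembrolizumab after CTL019/CTL119. This endpoint will be met if" no more than 30% "of patients develop toxicity resulting discontinuation of pembrolizumab". Section 4.2.3.1 uses the same limit to define safety, as at most 30% "of patients experiencing toxicities resulting in discontinuation of pembrolizumab". Sections 3.1 and 8.1.1 state it as the hypothesis. The planned size is "12 evaluable subjects".

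**Method.** The synopsis says the safety endpoint is assessed with a Bayesian monitoring rule. Section 8.1.1 gives the aim: "We will use a Bayesian monitoring rule to assure that the failure rate is no greater than 30" per cent. On the model, "we will assume a non-informative Beta(1, 1) prior distribution for the failure rate". On the action, if there is "at least a 97.5% chance that the failure rate is greater than 30%, we will stop the study". The printed boundaries are "3/3, 3/4, 4/5, 4/6, 5/7, 5/8, 6/9, 6/10, 7/11, 7/12".

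**Not stated.** No section gives an end-of-trial interval, posterior probability or test for concluding that the rate is 30% or less.

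**The concern.** The only inferential rule points one way. It asks for 97.5% posterior probability before concluding that the rate is too high. The favourable conclusion has a numerical limit but no measure of uncertainty. A rule that stops only on strong evidence of excess toxicity cannot assure that the rate is acceptable, because completing the trial shows only that such evidence did not accumulate.

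What is at stake is the strength of the primary safety conclusion. Section 4.2.3.1 says that pembrolizumab might reactivate quiescent CAR T cells and add toxicity, so how well 12 patients can exclude a rate above 30% is a central question. Monitoring of participants during the trial is not affected by this point.

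**Working it through.** **Inputs.** From Section 8.1.1: the Beta(1,1) prior, the 0.30 limit, the 97.5% cut-off and the printed boundaries. From the synopsis: n = 12 and the at-most-30% criterion. Since 3/12 = 25% and 4/12 = 33%, the criterion means at most 3 failures.

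**1. The plan's own boundary.** After x failures in n patients the posterior is Beta(1+x, 1+n−x), and Pr(FR > 0.30) = Pr(Bin(n+1, 0.30) ≤ x). At 7/12 this is 0.982 and at 6/12 it is 0.938, so 7/12 is the correct final boundary. Seven of the ten printed entries are the exact 97.5% boundaries. The other three fall just short: 3/4 (0.9692), 4/6 (0.9712) and 5/8 (0.9747). That is a separate matter and does not affect the n = 12 posteriors.

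**2. Posterior at 12 evaluable patients.** For 3/12, Pr(FR > 0.30) = Pr(Bin(13, 0.30) ≤ 3) = 0.0097 + 0.0540 + 0.1388 + 0.2181 = 0.4206. So Pr(FR ≤ 0.30) = 0.579.

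| Failures | Observed rate | Pr(FR ≤ 30%) | Pr(FR > 30%) | Status under the plan |
|---|---|---|---|---|
| 0/12 | 0% | 99.0% | 1.0% | met |
| 1/12 | 8.3% | 93.6% | 6.4% | met |
| 2/12 | 16.7% | 79.8% | 20.2% | met |
| 3/12 | 25.0% | 57.9% | 42.1% | met |
| 4/12 | 33.3% | 34.6% | 65.4% | not met, not stopped |
| 5/12 | 41.7% | 16.5% | 83.5% | not met, not stopped |
| 6/12 | 50.0% | 6.2% | 93.8% | not met, not stopped |
| 7/12 | 58.3% | 1.8% | 98.2% | stop |

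The 95% credible interval at 3/12, from the 2.5% and 97.5% quantiles of Beta(4,10), is 9.1% to 53.8%. The exact 95% confidence interval is 5.5% to 57.2%.

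**3. Chance of meeting the criterion.** Let X be the number of failures in 12. Of the 220 orderings with X = 3, four have all three failures among the first four patients and stop at 3/3 or 3/4. So P(met) = P(X ≤ 2) + P(X = 3) × 216/220.

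- True rate 40%: 0.0834 + 0.1419 × 216/220 = 0.223
- True rate 50%: 0.0193 + 0.0537 × 216/220 = 0.072

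**4. All outcomes, with the printed boundaries applied patient by patient.**

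| True rate | Met (≤3/12) | Completes at 4 to 6/12 | Stopped |
|---|---|---|---|
| 30% | 48.8% | 37.7% | 13.4% |
| 40% | 22.3% | 46.4% | 31.3% |
| 50% | 7.2% | 37.8% | 55.0% |

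At a true rate of 40% the trial runs to completion 69% of the time (22.3% + 46.4%).

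**5. Event and denominator.** The synopsis counts discontinuation for toxicity. Section 8.1.1 counts Grade 3 or higher non-hematologic toxicity leading to discontinuation, and also related Grade 4 non-hematologic toxicity or cytokine release syndrome, but then labels FR as the discontinuation rate. It first calls everyone with one dose evaluable, then limits the denominator to patients with at least four doses or with toxicity. Section 5.8 allows replacement and leaves early non-toxicity withdrawals out of the toxicity analysis. This can move the cut-off. As an illustration, if two replaced patients stayed in a one-dose denominator of 14, then 4/14 = 28.6% would also meet the criterion. Its posterior Beta(5,11) gives Pr(FR > 0.30) = Pr(Bin(15, 0.30) ≤ 4) = 0.515.

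**The case against.** **The criterion may not be a bare observed proportion.** A reader might infer that the plan expressly declares safety from the point estimate alone. The text does not go that far. The synopsis never says that the 30% is the observed rate, it says the endpoint is assessed by the monitoring rule, and Section 2.1 adds the rate of treatment-related adverse events to the safety endpoint. This stands as a limit on the wording. It does not close the gap. If 30% means the true rate, there is no success rule. If the monitoring rule is the assessment, 6/12 passes.

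**The 49% at a true rate of 30% is not an error rate.** The hypothesis is a rate of 30% or less, so it is true at exactly 30%. Only the figures at 40% and 50% describe false declarations. This stands.

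**At 3/12 the model still leans towards the target.** It puts 58% on a rate of at most 30%, with posterior mean 4/14 = 28.6%. This stands: the criterion does not point the wrong way, but it does not establish the claim.

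**Different bars for stopping and for success can be legitimate.** A high bar for halting and a looser one for an early-phase target serve different purposes, and wide uncertainty is the price of 12 patients. The asymmetry alone is therefore no defect. What remains is that the plan says the rule will assure the limit and attaches no uncertainty to the favourable conclusion.

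**Reporting is not restricted to a label.** One might infer that 0/12 and 3/12 would be reported identically. No section says that counts would be withheld. Equally, none requires the interval or the posterior probability.

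**Conclusion.** The point holds in this form: the plan has a criterion for calling safety met and a rule for stopping on excess toxicity, but neither quantifies support for a rate of 30% or less. At the worst qualifying result, 3/12, that support is 58%. A true rate of 40% or 50% would meet the criterion 22% or 7% of the time. Between 4/12 and 6/12 the plan gives no conclusion, while the probability of a rate above 30% rises from 65% to 94%.

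These figures assume exactly 12 evaluable patients, assessed one at a time against the printed boundaries, the Beta(1,1) prior, and one event definition shared by the criterion and the model. The last is not yet true of the documents. It would be wrong to conclude that 3/12 shows the regimen to be unsafe, or that the 30% limit or the sample size is itself at fault. The change affects what the primary safety result can claim and should be made before the final analysis.

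**What to change.** Keep the sample size, the 30% limit and the stopping rule. In Section 8.1.1:

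- Add: *The final failure rate will be reported with its 95% credible interval and Pr(FR ≤ 0.30 | data) from the Beta(1,1) model. An observed rate of 30% or less will be described as consistent with, but not as establishing, a true rate of 30% or less. Completion without stopping will not be taken as evidence that the rate is 30% or less.*
- Replace the statement that the rule will assure the limit with one saying that it stops the trial on strong evidence of a rate above 30%.
- Use one failure definition and one denominator for the criterion, the monitoring rule and the final estimate. The synopsis, Section 5.8 and Section 8.1.1 must be reconciled on both.

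Amend the synopsis to match. Reporting the posterior also covers 4/12 to 6/12, where the plan now says nothing.

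The cost is a few sentences, one line of output and a less strong safety claim. The changes to reporting and wording leave the cut-off and the operating characteristics above as they are. Settling the event and denominator may shift both.

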2.0 TRIAL DESIGN

2.1 Trial Design

This is a single center, open label trial of pembrolizumab in patients failing to respond to or relapsing after anti-CD19 chimeric antigen receptor modified T cell therapy (CTL019/CTL119) for relapsed or refractory CD19+ lymphomas.

Eligible patients will have CD19+ diffuse large B-cell, follicular, or mantle cell lymphomas with no available curative treatment options, a limited prognosis of several months to <2 years anticipated survival with currently available therapies, and progressive or relapsed disease after a single intravenous dose of $5 \times 10^8 \pm 20\%$ CTL019/CTL119 administered on our currently enrolling clinical trial (NCT02030834). We anticipate enrollment of 12 total patients onto the present trial for patients not responding to, or relapsing after, CTL019/CTL119.

[figure not shown]
The safety and efficacy of pembrolizumab in this group of patients will be determined using a fixed dose of 200mg IV. This dose was previously well-tolerated and effective for treatment of patients with metastatic melanoma and NSCLC. The primary safety endpoint will be determined by assessing the rate of pembrolizumab discontinuation as well as the rate of occurrence of treatment-related adverse events (AEs), defined as NCI CTCAE version 5 grade ≥ 3 AEs are possibly, probably, or definitely related to study treatment or grade 4 cytokine release syndrome. Secondary efficacy endpoints will be assessed, including overall response rate (ORR) and progression-free survival (PFS).

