3.2 Secondary Objectives & Hypotheses

(1) Objective: To describe the overall response rate (ORR) at 3 months to pembrolizumab in patients failing to respond to or relapsing after CTL019/CTL119 for relapsed or refractory CD19+ lymphomas. To describe the clinical efficacy of pembrolizumab, including progression-free survival, disease-free survival, event-free survival, response duration, and overall survival (Cheson, 2007) in patients failing to respond to or

This document is confidential and the property of the University of Pennsylvania. No part of it may be transmitted, reproduced, published, or used by other persons without prior written authorization from the regulatory sponsor.

relapsing after CTL019/CTL119. Efficacy comparisons will be made for ORR between CTL019/CTL119 and pembrolizumab.

Hypothesis: Pembrolizumab will enhance the efficacy of CTL019/CTL119 in patients failing to respond to or relapsing after CTL019/CTL119 for relapsed or refractory CD19+ lymphomas (John, 2013).

- (2) **Objective:** To describe the immunophenotypic and cytokine profiles of chimeric antigen receptor modified T cells in these patients before and after therapy with pembrolizumab

Hypothesis: Immunophenotypic profiles of tumor cells and chimeric antigen receptor modified T cells obtained pre and post pembrolizumab therapy will identify patients for whom pembrolizumab will enhance efficacy.

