8.1.2 Secondary Objectives & Hypotheses

Any patient who receives at least one dose of pembrolizumab will be included in efficacy analyses.

(1) Objective: To describe the overall response rate (ORR) to pembrolizumab in patients failing to respond to or relapsing after anti-CD19 chimeric antigen receptor modified T cell therapy for relapsed or refractory CD19+ lymphomas.

Methodology: For efficacy, a sample size of 12 patients achieves an 80% power to detect a difference (P1 0.35 – P0 0.05) of 0.30 using a one-sided binomial test for ORR. The target of significance level is 0.05. This response rate prediction of 35% is based on the reported 28% response rate reported for nivolumab, another anti-PD1 blocking antibody, in patients with B cell lymphoma. This also assumes that a 5% response rate would be seen if pembrolizumab does not have efficacy in this population. If the response rate is 3 or more, the hypothesis that the ORR is ≤ 0.05 is rejected. If the number of responses is 2 or less, the hypothesis that ORR is ≥ 0.35 .

Hypothesis: The response rate after pembrolizumab will be 3 or more, allowing us to reject the null hypothesis that pembrolizumab after CTL019/CTL119 has an ORR ≤ 0.05

(2) Objective: To describe the clinical efficacy of pembrolizumab, including progression-free survival, disease-free survival, event-free survival, response duration, and overall survival (Cheson, 2007) in patients failing to respond to or relapsing after anti-CD19 chimeric antigen receptor modified T cell therapy for relapsed or refractory CD19+ lymphomas. Efficacy comparisons will be made with both most recent prior therapy as well as with CTL019/CTL119.

Methodology: Kaplan Meier survival analysis will be used to estimate progression-free survival, event-free survival, response duration, and overall survival. For patients with initial responses to both CTL 019 and pembrolizumab, progression-free survival, event-free survival, and response duration, patients' response to CTL 019 therapy will be compared to their response to pembrolizumab using the log-rank test, with $p \leq 0.05$ considered statistically significant.

Hypothesis: Pembrolizumab will enhance the efficacy of CTL019/CTL119 in patients failing to respond to or relapsing after chimeric antigen receptor modified T cell therapy for relapsed or refractory CD19+ lymphomas.

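### The Trial Summary makes 3-month ORR a primary endpoint with a pass mark of 35% (5 of 12), but Section 8.1.2 makes it secondary and rejects the null at 3 of 12, and the stated 80% power belongs to that second rule

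*Combined protocol and SAP*

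**What the plan says.** **Trial Summary (Section 1.0), Objectives row.** Efficacy is item 2 under the primary endpoints: "This endpoint will be met if the ORR at 3 months is" at least 35%.

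**Trial Summary, Statistical methodology row.** Only safety appears under the primary endpoints. Under the secondary endpoints the row says "ORR will be assessed using a one-sided binomial test".

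**Sections 2.1, 3.1 and 3.2.** Section 2.1 names ORR among the secondary efficacy endpoints. Section 3.1 has safety as its only primary objective. The first secondary objective in Section 3.2 is "To describe the overall response rate (ORR) at 3 months to pembrolizumab".

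**Section 8.1.2 (secondary objectives in the analysis plan).** The objective is "To describe the overall response rate (ORR) to pembrolizumab in patients failing to respond" or relapsing after the CAR T-cell product, with no time point. The design statement is that "a sample size of 12 patients achieves an 80% power to detect a difference" between P1 = 0.35 and P0 = 0.05, with a one-sided binomial test and a target significance level of 0.05. The decision rule begins "If the response rate is 3 or more, the hypothesis that the ORR is" at most 0.05, and that hypothesis is then rejected. The analysis set is wide: "Any patient who receives at least one dose of pembrolizumab will be included in efficacy analyses".

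**The concern.** The documents disagree on two things: whether ORR is primary or secondary, and how many responders count as success. The Summary compares the observed rate with 35%. Section 8.1.2 tests against 5% and uses 35% as the rate at which power is calculated. An observed rate at or above the assumed true rate is a much harder target than rejection of the null, so these are different rules with different operating characteristics.

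Nothing in the text says which criterion governs, or that both must be met. With 3 or 4 responders of 12, one section supports a report that the null was rejected and another a report that a primary endpoint was missed. The trial is single-arm and open-label, so the choice between them could be made once the responses are known.

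**Working it through.** **Inputs.** n = 12, P0 = 0.05, P1 = 0.35, one-sided alpha 0.05, 80% power and rejection at 3 or more responders (all Section 8.1.2); pass mark of at least 35% (Section 1.0, Objectives). X is the number of responders, binomial(n, p).

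**1. Reproduce the plan's sample size.** For X ≥ 3 of 12:

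- Alpha = 1 − [0.95^12 + 12(0.05)(0.95^11) + 66(0.05²)(0.95^10)] = 1 − (0.5404 + 0.3413 + 0.0988) = 0.0196 (from unrounded terms).
- Power at 35% = 1 − [0.65^12 + 12(0.35)(0.65^11) + 66(0.35²)(0.65^10)] = 1 − (0.0057 + 0.0368 + 0.1088) = 0.8487.

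At n = 11 with the same cut-off, alpha is 0.0152 and power 0.7999, just short of 80%. So 12 is the smallest n with exact alpha at most 0.05 and power at least 80%. The sample size was evidently built on the 3-responder rule, and the 80% claim is met.

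**2. Convert the Summary pass mark to a count.** 0.35 × 12 = 4.2, so 5 responders are needed (4/12 = 33.3%, 5/12 = 41.7%).

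**3. Operating characteristics of the two rules at n = 12.**

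| Rule | Type I error at ORR 5% | Power at ORR 35% |
|---|---|---|
| Section 8.1.2: X ≥ 3 | 0.0196 | 84.9% |
| Summary: X ≥ 5 | 0.0002 | 41.7% |

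Setting P(X ≥ 5 \| 12, p) = 0.80 gives p ≈ 0.497, so the Summary rule would need a true ORR near 50% for 80% power.

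**4. How often the rules conflict.** They disagree when X is 3 or 4. At a true ORR of 35%:

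- P(X = 3) = 220(0.35³)(0.65^9) = 0.1954
- P(X = 4) = 495(0.35⁴)(0.65^8) = 0.2367
- Sum = 0.4321

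The probability is 47.1% at a true ORR of 28% (the nivolumab rate cited in Section 8.1.2) and 0.0196 − 0.0002 = 1.9% at 5%.

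**5. What the conflicting results would look like.**

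| Responders | Observed ORR | One-sided p against 5% | Exact 95% CI | Section 8.1.2 | Summary |
|---|---|---|---|---|---|
| 3 of 12 | 25.0% | 0.0196 | 5.5% to 57.2% | Null rejected | Not met |
| 4 of 12 | 33.3% | 0.0022 | 9.9% to 65.1% | Null rejected | Not met |

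**6. Minor: denominator.** Section 5.8 allows some dosed patients to be replaced, and Section 8.1.2 keeps every dosed patient in the efficacy analyses, so n can exceed 12. With the cut-off fixed at 3, alpha is 0.0429 at n = 16 and 0.0503 at n = 17. The rule therefore fails only with five or more dosed and replaced patients.

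**The case against.** The best defence is that the Summary line is a leftover. Section 3.1, the endpoint rationale in Section 4.2.3.1 and Section 8.1.1 all have safety as the only primary objective, and Section 8.1.2 is the designated analysis plan with an explicit rule. On that reading the analysis plan governs, and 3 or 4 responders simply reject the null. Section 8.1.2 also mentions 0.35 in its rule for 2 or fewer responders. That sentence lacks its verb, and rejection of an ORR of 35% or more is the natural completion. The Summary's 35% could then be loose shorthand for the same two-hypothesis rule. Finally, ORR is described as a descriptive objective in a 12-patient trial, and the Summary itself states no power.

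Part of this stands. The weight of the text favours secondary status, and the fix follows it. The Summary does not itself attach the 80% to its pass mark; that figure appears only beside the 3-responder rule. The missing time point in Section 8.1.2 is a small gap, since Section 3.2 says 3 months and Section 6.3 schedules imaging at week 12. The denominator point has little practical effect.

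The core is untouched. The Summary says in terms that the endpoint is met at an observed ORR of 35% or more, and no clause gives Section 8.1.2 precedence. In the 2-or-fewer sentence 0.35 is still the design alternative for the true rate, so it does not turn the Summary's pass mark into 3 of 12.

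**Conclusion.** The concern holds. The plan gives ORR two statuses and two success criteria: 5 of 12 in the Summary and 3 of 12 in Section 8.1.2. Only the second matches the stated design, with exact alpha 0.0196 and power 84.9%; the first has 41.7% power at the design rate. The criteria give opposite answers with probability 43.2% if the true ORR is 35%. These figures assume exactly 12 patients in the efficacy analysis and independent responses with a common rate. The conclusion that nothing reconciles the two rules rests on the text available for review, which lacks a short portion directly after Section 8.1.2. Because endpoint status and a decision threshold are affected, this must be corrected before the response data are interpreted.

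**What to change.** Once the sponsor has confirmed its intent:

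1. In Section 1.0, remove the 35% pass mark and move ORR to the secondary endpoints in the Objectives row. Suggested wording: *ORR at 3 months (secondary). The null hypothesis that ORR is 5% or less is rejected by a one-sided exact binomial test if 3 or more of 12 treated patients respond. Design alternative 35%; exact alpha 0.020, power 85%.*
2. In Section 8.1.2, add the 3-month time point to the ORR objective and to the decision rule, and complete the sentence on 2 or fewer responses.
3. Minor: tie the cut-off to the number treated. Three remains valid up to n = 16; four is needed from n = 17.

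If the sponsor did intend an observed ORR of at least 35% as a further requirement, say that both criteria must hold, that the second means 5 of 12, and that its power is 42% at a true ORR of 35%.

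The cost is wording in Sections 1.0 and 8.1.2. Sample size, null, alpha and the cut-off at n = 12 do not change.
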